### B2. SIGNIFICANCE AND BACKGROUND FOR THE STUDY

Advanced chronic liver disease/cirrhosis creates a state of relative immune-compromise, and, indeed, infections are a key precipitant of clinical decline in patients with cirrhosis. Specifically, infections of any kind are a common cause of acute on chronic liver failure (ACLF) and complicate 20-40% of hospital admissions of patients with cirrhosis. Although other pathogens are also important, the vast majority of infections in patients with cirrhosis are of bacterial origin. In other high-risk hospitalized patient populations, early initiation of antibiotics has been shown to reduce the need for intensive care unit (ICU) admission and short-term mortality. Unfortunately, the presentation of infection in patients with cirrhosis is protean and may be subtle. Diagnosis may be delayed by the absence of classic signs of infection such as fever and absolute leukocytosis. Vital diagnostic studies, such as paracentesis or other culture (blood, urine, or sputum) may be delayed or may not yield results until days after presentation. Delaying antibiotics until such studies result is inadvisable in patients with infection; however, empiric administration of antibiotics to all patients with cirrhosis admitted to the hospital would result in waste and increased risk of antibiotic resistance, *Clostridium difficile* infection, and other adverse effects. Sub-groups of patients with cirrhosis are already known to benefit from empiric/prophylactic antibiotics including those with acute upper gastrointestinal hemorrhage and those with increased risk of spontaneous bacterial peritonitis. The risk of infection increases with more advanced cirrhosis, as marked by higher Model for End-stage Liver Disease – Sodium (MELD-Na).

There are also biomarkers of systemic infection that, although not specific, may be used to identify patients more likely to have an active infection and thus allow more targeted use of empiric antibiotics. Specifically, increase in serum C-reactive protein (CRP, >25 mg/L) and Procalcitonin (>0.5 ng/mL) are associated with acute bacterial infection.

These factors may permit identification of patients who would benefit from prophylactic/empiric antibiotics. There has not, however, been investigation of the effect of prophylactic antibiotics on hospitalized patients with advanced cirrhosis beyond the sub-populations described above.

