**B3. DESCRIPTION OF RESEARCH PROTOCOL****A. Study Design – Overview, Methods, Procedures**

This is a blinded, randomized, placebo-controlled pilot trial to determine feasibility of subject identification, rate of enrollment, and data collection, including specimen processing, for a future, larger randomized trial of the effect of empiric antibiotics for all patients with advanced cirrhosis admitted to the hospital without an existing indication for new antibiotic use. Specifically, we will assess the incidence of infection after the time of enrollment and associated outcomes. Patients will be randomized to receive either ceftriaxone or placebo (normal saline). Study drug will be delivered in masked vials for daily IV administration.

**Case finding and Screening:** Eligible patients will be identified in the emergency department or by admitting physicians upon their initial medical assessment or by study personnel via daily review of the inpatient hepatology ward and consultative service census. Study personnel will screen each potential subject by review of medical record for potential eligibility.

**Consent:** If a patient meets basic eligibility criteria, a study investigator will meet with the potential subject/LAR to review the study protocol and obtain informed consent. Screening measures will be completed following consent and the balance of the baseline measures will be completed.

**Extended Screening/Baseline:** Evaluation for undiagnosed infection will be completed following consent and prior to randomization including: chest x-ray, venous blood culture, urine culture- all, if not already performed via routine care. These studies may be deferred if they have been done within 7 days of enrollment and there has been no change in clinical status. Subjects with infection identified upon enrollment will be excluded from further participation and have further treatment directed by their standard clinical providers.

Each subject's medical record will be reviewed to determine the presence or absence of diuretic-resistant ascites (defined by history of TIPS, large volume paracentesis within the past 3 months despite diuretics, or intolerance of diuretics).

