Each subject's medical record will be reviewed to determine the calculated baseline CLIF-C ACLF score (Chronic Liver Failure Consortium (CLIF-C) Acute on Chronic Liver Failure). This will be computed using data (laboratory and physical examination) collected as part of standard of care. These data points include:

- bilirubin,
- creatinine,
- INR,
- West Haven grade of encephalopathy,
- mean arterial pressure, and
- peripheral oxygen saturation (SpO2).

A peripheral or central venous blood sample will be taken after consent is obtained. Approximately thirty milliliters (2 tablespoons) of whole blood will be collected. We will measure serum procalcitonin and C-reactive protein for the research study and store remaining specimen for potential future testing.

Patients will be excluded if there is a clinical indication for new treatment with antibiotics, e.g. upper gastrointestinal hemorrhage or apparent infection. Standard of care treatment will never be delayed.

**Randomization:** Each subject will be randomized to receive antibiotic treatment (ceftriaxone) or placebo (normal saline). Randomization will be blinded to patients, study investigators, and study staff. Only the BIDMC Research pharmacist will know treatment assignment. Randomization will be stratified by the presence of either serum creatinine  $\geq$  2.0 mg/dL and/or diuretic-refractory ascites.

**Study Intervention:** The research pharmacy staff will provide antibiotic or placebo in the form of masked vials of intravenous solution. This will consist of either 1 gr ceftriaxone or an equal volume of normal saline (approximately 100 mL). This administration will begin as soon as possible after enrollment and will be repeated once daily. If a subject is prescribed an equivalent intravenous antibiotic during the hospitalization (i.e., ceftriaxone, piperacillin/tazobactam, or a carbapenem), the study-treatment (ceftriaxone/placebo) will be withheld on those days. If the clinically prescribed antibiotic is subsequently discontinued prior to discharge, the study-treatment/placebo may be resumed. Study treatment will be discontinued on study treatment day 7, or at the time of discharge or liver transplantation, if such events occur earlier than treatment day 7.

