## B. Statistical Considerations

**Sample Size Justification:** We estimate there will be a small prevalence of occult infection among patients who are believed to be eligible after initial screening is completed. Patients with identified infection at the time of enrollment will not be randomized and instead be treated as per standard of care at the discretion of the medical staff. We estimate there may be 5-10 such patients who are thus enrolled but not randomized.

We aim to randomize a total of 40 subjects, assigned to active intervention vs. placebo; hence as many as 50 may be screened / consented to determine eligibility. This is a pilot study intended to assess feasibility of patient identification, administration of required testing and enrollment processing, and the rate thereof. The magnitude of observed effect will permit sample size estimation for a larger, more definitive study which we hope to complete subsequently. It is unknown how many subjects will need to be screened to complete this planned enrollment. We will also obtain information on the dropout rate and/or rate of use of therapeutic antibiotics which may alter enrollment goals for a future study.

**Data Analysis:** As stated elsewhere, the proposed study is a pilot study, not intended to provide definitive results. However, there are multiple outcomes of interest that will be recorded in order to permit planning of a future study.

The primary outcome is incident bacterial infection identified after randomization

screening (as defined below).

Secondary outcomes include:

1. In-hospital mortality;
2. 30-day mortality;
3. Incident acute on chronic liver failure (ACLF) defined as two or more of:
  - Grade 3-4 hepatic encephalopathy,
  - Need for renal replacement therapy,
  - Need for mechanical ventilation,
  - Need for vasopressors, or mean arterial pressure (MAP) <60 mmHg, or decrement of >40 mmHg in systolic blood pressure after volume resuscitation.
4. Change in calculated CLIF-C ACLF score;
5. Length of stay (LOS) after randomization;
6. Intensive Care Unit (ICU) transfer after randomization;
7. C difficile infection (positive stool polymerase chain reaction (PCR) or toxin-assay in the setting of diarrhea);
8. Increment in MELD-Na  $\geq 3$  points between randomization and discharge;
9. Acute kidney injury (increase in creatinine  $\geq 0.3$  mg/dL in 48 hr or  $>50\%$  from baseline (within previous 3 months) occurring after randomization;
10. Variceal hemorrhage.

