Covariates recorded/measured

- Procalcitonin at enrollment
- C-reactive protein at enrollment
- Other antibiotic use in-hospital (type and duration)
- Fungal infections (by positive culture) or use of systemic anti-fungal medications.

We will monitor daily for the incidence of the outcomes above via review of the medical record and discussions with the inpatient providers (when necessary). For any subject with a positive culture result, the site, organism, and antibiotic susceptibility will be recorded when available.

Infection definitions

- Bacteremia (positive blood culture not felt to be a skin flora contaminant)
- Spontaneous bacterial peritonitis (ascites PMN count  $>250/\mu\text{L}$  or positive ascites culture in the setting of new abdominal pain, or unexplained leukocytosis, fever, hypotension, fever, acute kidney injury, or exacerbation of hepatic encephalopathy, i.e., increase in West Have grade)
- Pneumonia: Pulmonary infiltrate on chest x-ray (CXR) or computed tomography (CT) in the presence of A) respiratory symptom(s) (cough, pleuritic pain, or dyspnea) or B) auscultation findings, abnormal body temperature ( $>38\text{C}$  or  $<36\text{C}$ ), or newly abnormal leukocyte count  $>10,000/\text{microL}$  or  $<4,000/\text{microL}$  (if baseline leukocyte count  $>4,500/\text{microL}$ ).
- Skin or Soft Tissue Infection (SSTI): Superficial erythema, warmth, or fluctuance in the

skin/soft tissues felt to be secondary to infection by the inpatient team, excluding mild superficial thrombophlebitis from IV catheter insertion

- UTI: Urine leukocytes  $> 10/\text{hpf}$ , bacteruria, positive urine culture, urinary leukocyte esterase or nitrite in the presence of symptoms/signs of infection (dysuria, unexplained increased urinary frequency, fever, or leukocytosis)
- Other infections as identified by the primary medical team

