For purposes of analysis, deidentified subject clinical data documenting the metrics above will be stored in a password protected file within the BIDMC network. Analysis will be conducted at BIDMC using R-studio software. There are no additional statistical consultants currently affiliated with this study. Descriptive statistics will include the incidence of the primary and secondary categorical outcomes in each arm with comparison via Chi-square test or Fisher's exact test for rare events. As noted elsewhere, we do not anticipate this study will provide sufficient statistical power to demonstrate statistically significant differences between groups, but we will need to have an idea of the magnitude of effect prior to planning such a study and hope to obtain this information here.

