#### ***Inclusion Criteria:***

- Age  $\geq 18$
- Cirrhosis, as defined by liver biopsy (completed as standard care) or a composite assessment of available results from imaging or elastography, prior records, and laboratory studies
- MELD-Na  $\geq 18$  (Model for End Stage Liver Disease-Sodium, incorporating components of serum sodium, bilirubin, International Normalized Ratio (INR), and creatinine

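### Randomization is stratified by creatinine or refractory ascites, but no planned analysis uses the stratum: no bias, only a little unused precision

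*Combined protocol and SAP*

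**What the plan says.** Under Randomization in B3.A: "Randomization will be stratified by the presence of either serum creatinine" of at least 2.0 mg/dL and/or diuretic-refractory ascites. This is read here as one binary factor, hence two strata. The ascites part is established before randomization: under Extended Screening/Baseline each subject's "medical record will be reviewed to determine the presence or absence of diuretic-resistant ascites".

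The Data Analysis text in B3.B reports the "incidence of the primary and secondary categorical outcomes in each arm with comparison via Chi-square test", or Fisher's "exact test for rare events". No stratified or adjusted analysis appears anywhere. The list headed "Covariates recorded/measured" holds procalcitonin, C-reactive protein, other antibiotic use and fungal infection or antifungal use; the stratification factor is not on it.

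On the use of the result, the Sample Size Justification says: "The magnitude of observed effect will permit sample size estimation for a larger, more definitive study". Data Analysis repeats that the study is not expected to have adequate power and that an idea of the effect's magnitude is wanted.

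**The concern.** When randomization is stratified by a factor that predicts the outcome, the treatment estimate varies less between hypothetical repeats of the trial. An unstratified standard error does not show this: the interval comes out too wide and the test is conservative. An analysis by stratum recovers the difference.

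Whether there is anything to recover depends on how well the factor predicts infection. The documents give only indirect support. B2 says: "The risk of infection increases with more advanced cirrhosis, as marked by higher Model for End-stage Liver Disease", and the inclusion criteria describe that score as "incorporating components of serum sodium, bilirubin, International Normalized Ratio (INR), and creatinine". B2 also names patients at increased risk of spontaneous bacterial peritonitis as a group known to benefit from prophylaxis, and B3.B diagnoses that infection from ascitic fluid and lists it among the infection definitions. None of this gives a figure. Two features may weaken the link: every subject already has MELD-Na of at least 18, and infection detected at enrollment is excluded before randomization.

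At stake is the precision of the effect estimate carried into planning the next trial. No decision in this pilot rests on the p-value.

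**Working it through.** **Inputs from the documents.** 40 randomized; two strata; binary primary outcome (incident bacterial infection); unstratified Chi-square or Fisher test. The figure of 40 has no event rate, effect size or power behind it, so there is no calculation to reproduce.

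**Assumptions, because the documents are silent.** Allocation 1:1 (20 per arm) with the same ratio in both strata; two strata of 20, so 10 per arm in each; two-sided 5% level; treatment risk ratio (RR) 0.4 or 1; rare taken as a smallest expected count below 5 (9 or fewer events in total); control risks with and without the factor as in the table.

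**Step 1: point estimate.** The Mantel-Haenszel risk difference is Σ w_k d_k / Σ w_k, with w_k = n_Tk n_Ck / n_k. Here each w_k = 10×10/20 = 5, so it equals (d_1 + d_2)/2, which is the crude difference. With balanced strata the planning input does not move; only its interval does.

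**Step 2: interval at RR 1, in closed form.** With a share of one half in each stratum and mean risk p, the factor explains R² = 0.25(p_1 − p_0)² / [p(1 − p)] of the outcome variance. The crude half-width is 1.96√[2p(1 − p)/20], and the stratified one is that times √(1 − R²). For 50/10%: p = 0.30, R² = 0.04/0.21 = 0.190, crude 28.4 points, stratified 28.4 × 0.900 = 25.6, a gain of 2.8. Enumerating every possible outcome gives average half-widths of 27.8 and 24.8, a gain of 3.0. Over the four prognostic scenarios the enumerated gain is 0.4 to 3.0 points.

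**Step 3: interval at RR 0.4, by enumeration.** Crude half-width: 1.96√[p_T(1 − p_T)/20 + p_C(1 − p_C)/20]. Stratified half-width: 1.96√V, with the Sato variance V = [RD·ΣP_k + ΣQ_k]/(Σw_k)². For equal arms of n per stratum with a_k treated and c_k control events, P_k = (c_k − a_k)/4 and Q_k = [a_k(n − c_k) + c_k(n − a_k)]/(4n). Both half-widths are averaged over all outcomes.

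**Step 4: power at RR 0.4, by enumeration.** The plan's rule (Fisher if rare, otherwise Chi-square) against its stratified counterpart (exact conditional Cochran-Mantel-Haenszel if rare, otherwise the uncorrected version).

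| Control risks, % | Stratum odds ratio | Half-width RR 0.4, crude vs stratified (points) | R² at RR 1 | Closed-form gain at RR 1 (points) | Power RR 0.4, planned vs stratified (%) |
|---|---|---|---|---|---|
| 40/10 | 6.0 | 22.3 vs 21.6 | 0.120 | 1.7 | 15.6 vs 15.8 |
| 50/10 | 9.0 | 23.9 vs 22.7 | 0.190 | 2.8 | 21.9 vs 23.0 |
| 40/20 | 2.7 | 23.9 vs 23.5 | 0.048 | 0.7 | 23.3 vs 23.2 |
| 30/15 | 2.4 | 21.4 vs 21.2 | 0.032 | 0.4 | 13.4 vs 13.4 |
| 25/25 | 1.0 | 22.3 vs 22.3 | 0 | 0 | 16.7 vs 16.7 |

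Before rounding, the RR 0.4 gain in the prognostic rows is 0.2 to 1.3 points. With strata of 12 and 28 (first four rows) power is 8.8 vs 8.5, 11.2 vs 11.9, 17.6 vs 16.8 and 10.1 vs 8.8%. Across both layouts, changing the test moves power by −1.3 to +1.1 points.

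**Step 5: validity.** Under no treatment effect the planned rule rejects in 2.0 to 4.5% of trials, never above 5%. In a separate simulation with stratum odds ratios of 1 to 10, the crude risk difference lay within 0.0013 of the truth throughout.

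**Step 6: if allocation is not blocked within strata** (400,000 simulated trials per scenario, RR 0.4, table order). The variance of the stratified relative to the crude estimate is 0.95, 0.91, 1.00, 1.01 and 1.03. The two estimates differ by a median of 0.7 to 2.7 points, against a crude standard deviation of about 12 points.

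**Step 7: cost in coverage.** In the balanced 20/20 runs (RR 0.4 and 1) the Mantel-Haenszel interval covers 93.1 to 94.4%, and the crude interval 93.2 to 95.8%.

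**The case against.** The case for leaving the plan alone is strong, and most of it stands. The study is a declared pilot with a descriptive comparison. The planned test is valid, the point estimate does not change when strata are balanced, and power barely moves even at a stratum odds ratio of 9. The plan names no effect measure and no confidence interval, so the crude interval above is a comparator and not something the sponsor has committed to. Part of the narrowing is paid for in coverage: at 50/10% and RR 0.4 it falls from 95.6 to 94.4%. The covariate list is weak evidence, since no planned analysis uses anything on it, and the Data Analysis text does not say that other summaries are ruled out.

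This settles the severity but does not remove the point. The plan makes the size of the effect an output for designing the next trial, so how precisely it is stated matters more than the p-value, and the stratum is already in hand.

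A reader might infer more, namely that an analysis that ignores the strata is biased or produces too many false positives. The documents do not support that: nothing suggests different allocation ratios in the two strata, and any error in the test is on the conservative side. Nor do they establish that the factor is a strong predictor of infection. The opposite claim, that nothing links ascites to infection, also goes too far given the references to spontaneous bacterial peritonitis in B2 and B3.B.

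**Conclusion.** The mismatch is real and minor. Randomization uses a stratum that no planned analysis uses; the consequence is unused precision, not a wrong answer. If the factor is prognostic, stratifying narrows the 95% half-width by 0.2 to 1.3 points at RR 0.4 and 0.4 to 3.0 points at RR 1, on half-widths of roughly 21 to 28 points. If it is not prognostic, there is no gain. The larger gains need a stratum odds ratio of about 6 to 9.

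These sizes rest on assumed stratum risks, two strata of 20, 1:1 allocation and two chosen risk ratios; the documents supply none of these. The absence of bias refers to the risk difference and assumes the same allocation ratio in both strata. It would be wrong to read this as a reason to replace the Chi-square or Fisher test.

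**What to change.** In Data Analysis (B3.B), add for the primary outcome: the Mantel-Haenszel risk difference with 95% confidence interval, stratified by the randomization stratum, reported alongside the planned unstratified comparison. The planned test stays as it is.

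The cost is one or two sentences. The stratum must be known for each subject before randomization, so no new data are needed. There are three statistical downsides:
- coverage slightly below nominal, about 93 to 94%;
- instability with few events (below about 5 in total there is almost nothing to gain, at most 0.3 points of half-width);
- about 3% of variance lost if the factor is not prognostic and allocation is unblocked.

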### **C. Subject Selection**

Potential subjects will be identified by attending hepatologists on the ward/consultation service during the course of clinical care and/or by study personnel via daily review of these patient lists in OMR. Patients meeting eligibility criteria below will be reviewed and approached to discuss the study, if appropriate.

#### ***Inclusion Criteria:***

- Age  $\geq 18$
- Cirrhosis, as defined by liver biopsy (completed as standard care) or a composite assessment of available results from imaging or elastography, prior records, and laboratory studies
- MELD-Na  $\geq 18$  (Model for End Stage Liver Disease-Sodium, incorporating components of serum sodium, bilirubin, International Normalized Ratio (INR), and creatinine

#### ***Exclusion Criteria:***

- Inability to obtain consent from subject or next of kin/legal authorized representative (LAR)
- Allergy to cephalosporins
- Pregnancy (due to limited prospective data regarding safety of ceftriaxone)
- Presence of ascites amenable to paracentesis without paracentesis performed as SOC for exclusion of infection
- Existing indication for new antibiotics, e.g. upper gastrointestinal hemorrhage or apparent infection
- Use of major immunosuppressive medications (e.g. prednisone 20 mg/day or greater, immunosuppression for solid organ transplant)
- History of recurrent *C. difficile* infection within the past year ( $>2$  episodes) or requiring prior fecal microbiota transplant (FMT)
- Enrollment in the study protocol during a previous admission

There are no specific limitations regarding gender or racial distribution of the planned population studied and as such, our intended sample will reflect a subset of these patients

without selection based on either parameter. The only exception to this is pregnant women will be excluded due to theoretical risk of adverse effect of ceftriaxone exposure (Pregnancy category B). Please note that is exceptionally rare to encounter a pregnant patient with this degree of chronic liver illness.

There are no specific requirements for contraception during this short study conducted with patients admitted to the hospital.

